14.4 Participant Confidentiality

The Investigator must ensure that the participant's privacy is maintained. On the CRF and other documents submitted to the Sponsor, participants will be identified by a participant study number only. Documents that are not submitted to the Sponsor (eg, signed ICF) should be kept in a strictly confidential file by the Investigator.

The Investigator shall permit authorized representatives of the Sponsor, regulatory agencies, and IRBs/IECs/REBs to review the portion of the participant's medical record that is directly related to the study. As part of the required content of informed consent, the participant must be informed that his/her records will be reviewed in this manner.

Applicable data privacy laws and regulations must be adhered to. The Investigator and the Sponsor are responsible for ensuring that sensitive information is handled in accordance with local requirements (eg Health Insurance Portability and Accountability Act [HIPAA]). Appropriate consent and authorizations for use and disclosure and/or transfer (if applicable) of protected information must be obtained.

14.5 Study Monitoring

The Investigator must allow the Study Monitors to periodically review, at mutually convenient times, during the study and after the study has been completed, all eCRFs and office, hospital, and laboratory records supporting the participation of each participant in the study (source data). The eCRFs and other documentation supporting the study must be kept up to date by the Investigator and the research staff at the investigative site. These study materials must be available for review by the Study Monitor, and/or other qualified representatives of the Sponsor, at each monitoring visit.

It is the monitor's responsibility to inspect the CRFs at regular intervals throughout the trial to verify adherence to the protocol, the completeness, accuracy and consistency of the data, and adherence to GCP guidelines.

The Investigator agrees to cooperate with the monitor to ensure that any problems detected during the course of these monitoring visits are resolved.

14.6 Case Report Forms and Study Records

The investigative site will use eCRFs to record all the protocol-specified data for each participant enrolled in this study. Entries made in the eCRF must be verifiable against source documents. Data reported in the eCRF that are derived from source documents should be consistent with the source documents or the discrepancies should be explained.

The Investigator will be responsible for reviewing all data and eCRF entries and will sign and date the designated pages in each participant's eCRF, verifying that the information is accurate.

14.7 Data Monitoring Committee

A DSMB will be established to assess participant safety at predetermined intervals during the study, and as needed. Refer to the DSMB Charter for further details. [REDACTED]

[REDACTED]

[REDACTED]

14.8 Data Generation and Analysis

The investigative site will use eCRFs to record all the protocol-specified data for each participant enrolled in this study. Entries made in the eCRF must be verifiable against source documents. Data reported in the eCRF that are derived from source documents should be consistent with the source documents or the discrepancies should be explained.

The Investigator will be responsible for reviewing all data and eCRF entries and will sign and date the designated pages in each participant's eCRF, verifying that the information is accurate.

14.9 Retention of Data

The Investigator must ensure that all records pertaining to the conduct of the clinical study, ICFs, drug accountability records, source documents, and other study documentation are adequately maintained for a period of 2 years after the last approval of a marketing application in an ICH region and until there are no pending or contemplated marketing applications in an ICH region or at least 2 years have elapsed since the formal discontinuation of clinical development of the study drug.

The Investigator must not destroy any records associated with the study without receiving approval from the Sponsor. The Investigator must notify the Sponsor in the event of accidental loss or destruction of any study records.

Whenever possible, an original recording of an observation must be retained as the source document. However, a photocopy of a record is acceptable provided it is legible and is a verified copy of the original document.

All eCRF data entered by the site (including audit trail), as well as computer hardware and software (for accessing the data), will be maintained or made available at the site in compliance with applicable record retention regulations. The CRO will retain the original eCRF data and audit trail.

14.10 Financial Disclosure

Financial Disclosure statements will be handled in a separate agreement apart from the protocol, kept on file, and submitted as applicable with any subsequent license application.

14.11 Publication and Disclosure Policy

The data generated in this clinical study are the exclusive property of the Sponsor and are confidential. Any publication of the results of this study must be authorized by the Sponsor. The Sponsor will have the opportunity to review any publications that arise from the Investigators before submission for publication. Any such review and approval of publications related to the study shall be made pursuant to the process agreed between the parties in the site's clinical trial agreement with Sponsor. Authorship on any publication of the results from this study will be based on contributions to study design, enrollment, data analysis, and interpretation of results.

APPENDIX 1 SCHEDULE OF EVENTS: PARTS B AND C

	Screening	Treatment					EoS / ET
	Visit 1	Visit 2	Visit 3	Visit 4	Visit 5	Visit 6	Visit 7
	Day -28 to Day -1	Baseline Day 1	Week 2 Day 14 (±2 days)	Week 4 Day 28 (±2 days)	Week 8 Day 56 (±3 days)	Week 12 Day 84 (±3 days)	Week 14 Day 98 (±3 days)
Informed consent	X						
Medical history	X						
Demographics (age, sex, race)	X						
██████████	■					■	
Serum pregnancy test	X						
Check inclusion and exclusion criteria	X	X					
Complete physical examination (including height and weight)	X						
Targeted physical examination		X	X	X	X	X	X
Randomization		X					
██████	■	■		■	■	■	■
██████	■						
DLco	X						
██████████	■	■	■	■	■	■	■
Vital signs (post 3 minutes, supine; approx 2 hrs post dose and around the time of the █████)	X	X	X	X	X	X	X
██ ██	■	■	■	■	■	■	■
Hematology (post 8-hour fast)	X	X	X	X	X	X	X
Clinical chemistry (post 8-hour fast) ^f	X	X	X	X	X	X	X
Coagulation (post 8-hour fast)	X	X	X	X	X	X	X
Pharmacokinetic sample plasma × 2 (predose and at least 2 hours postdose) ^g		X		X		X	X ^g
Pharmacokinetic nintedanib/pirfenidone sample plasma x 2 (predose and at least 2 hours post dose to PLN-74809) ^h		X		X		X	X

- [REDACTED]
- g [REDACTED] PLN-74809 levels will be measured. Actual PK sample collection time and dosing time will be recorded. If the participant discontinues the study early, a plasma sample for PK should be taken at the ET Visit if possible.
- h For participants receiving nintedanib/pirfenidone only; timed relative to PLN-74809 dosing.

Week 14 Visit through End of Study

(continued)	Treatment							EoS / ET	
	Visit 7	Visit 8	Visit 9	Visit 10	Visit 11 ^a	Visit 12 ^a	Week 48 / Unscheduled / End of Treatment Visit EoT ^{a,b}	End of Study Visit EoS	
	Week 14 Day 98 (±3 days)	Week 20 Day 140 (±3 days)	Week 24 Day 168 (±3 days)	Week 26 Day 182 (±3 days)	Week 32 Day 224 (±5 days)	Week 40 Day 280 (±5 days)	Final On- Treatment Visit	Final On- Treatment Visit + 2 weeks (±3 days)	
██████████			■						
Targeted physical examination	X	X	X	X	X	X	X	X	
██████	■	■	■	■	■	■	■	■	
██████████	■	■	■	■	■	■	■	■	
Vital signs (post 3 minutes, supine; approx 2 hrs post dose and around the time of the █████)	X	X	X	X	X	X	X	X	
██ ██ ██████	■	■	■	■	■	■	■	■	
Hematology (post 8-hour fast)	X	X	X	X	X	X	X	X	
Clinical chemistry (post 8-hour fast) ^h	X	X	X	X	X	X	X	X	
Coagulation (post 8-hour fast)	X	X	X	X	X	X	X	X	
Pharmacokinetic sample plasma × 2 (predose and at least 2 hours postdose) ^{f, i}			X						
Pharmacokinetic nintedanib/pirfenidone sample plasma x 2 (predose and at least 2 hours post dose to PLN-74809) ^{g, l}			X						
████████████████████			■						
████████████████████			■						
████████████████████			■						

^g For participants receiving nintedanib/pirfenidone only; timed relative to PLN-74809 dosing.

^h If the participant discontinues the study early, a plasma sample for PK should be taken at the ET Visit if possible (PK at ET visit can be collected at any point in visit).

ⁱ [REDACTED]

Controlled Quality Management Document

Sponsor: Pliant Therapeutics Inc.

Protocol Number: PLN-74809-IPF-202

STATISTICAL ANALYSIS PLAN. PHASE 2-3-4

Statistical Analysis Plan

A randomized, double-blind, dose-ranging, placebo-controlled Phase 2a evaluation of the safety, tolerability, and pharmacokinetics of PLN-74809 in participants with idiopathic pulmonary fibrosis (IPF) (INTEGRIS-IPF)

Protocol Number: *PLN-74809-IPF-202*

Protocol Version: *3.0*, [REDACTED]

SAP Version *2.0*, [REDACTED]

Addendum 1.0, [REDACTED]

Addendum 2.0, [REDACTED]

Addendum 3.0, [REDACTED]

Addendum 4.0, [REDACTED]

Addendum 5.0, [REDACTED]

Post Final database lock Addendum, [REDACTED]

[REDACTED]

Previous SAP Versions

SAP Version 1.0, [REDACTED]

Confidentiality Statement

This document is the property of [REDACTED] and may not be duplicated, copied, altered or removed from company without prior approval from [REDACTED] or in compliance with [REDACTED].

Controlled Quality Management Document		
	Sponsor:	Pliant Therapeutics Inc.
	Protocol Number:	PLN-74809-IPF-202
STATISTICAL ANALYSIS PLAN. PHASE 2-3-4		

SAP Amendments Before Database Lock for Parts A/B/C Week 12

Version	Issue Date	Section	Revision / Addition
2.0	17 June 2022	6.1.7	Definition of Efficacy Per Protocol Population was amended.
		6.2.4	Procedure for early termination assessments was defined.
		6.2.5	Handling of spirometry assessments was clarified.
		6.2.13	Compliance calculation was refined.
		6.2.17	Definition of electrocardiogram abnormalities was amended and clarified.
		6.6	Handling of DLCO lung function assessment at screening was clarified.
		6.6	Duration Since Diagnosis at Screening and Duration of Standard of Care at Randomization was defined and will be summarized in Participant Disposition.
		[REDACTED]	[REDACTED]
		6.11.1	Clarification added. FVC in mL will be analyzed.
		6.13	Clarification added. Result adjusted for dilution factor will be used.
		[REDACTED]	[REDACTED]
		6.15.1	Tabulations and listings for serious adverse events were added.
		6.15.2	Clarification added. Système International (SI) units will be used to report laboratory results.
		6.15.4	Definition of 'Confirmed Abnormality' was clarified.
		9	Changes to Planned Protocol Analyses was updated.
11	List of Tables, Figures and Listings was updated.		

Confidentiality Statement
This document is the property of [REDACTED] and may not be duplicated, copied, altered or removed from company without prior approval from [REDACTED] or in compliance with [REDACTED].

Controlled Quality Management Document		
	Sponsor:	Pliant Therapeutics Inc.
	Protocol Number:	PLN-74809-IPF-202
STATISTICAL ANALYSIS PLAN. PHASE 2-3-4		

SAP Amendments Post Database Lock for Parts A/B/C Week 12 and pre database lock for Part D Week 12

Version	Issue Date	Section	Revision / Addition
Addendum 1.0	02 Dec 2022	6.15.2	CTCAE grading for laboratory test parameters removed
		6.11.1	Added new pooled placebo groups and Wilcoxon rank sum test for FVC at Week 12
		7	Added text to clarify data cut off day for Part D interim
		11	List of Tables, Figures and Listings was updated.
Addendum 2.0	06 Dec 2022	11	List of Tables, Figures and Listings was updated.
Addendum 3.0	12 Dec 2022	11	List of Tables, Figures and Listings was updated.

SAP Amendments Post Database Lock for Parts A/B/C/D Week 12 and pre database lock for Part D Week 24

Version	Issue Date	Section	Revision / Addition
Addendum 4.0	31 Jan 2023		
		6.2.20	Addition of SAS code to determine outliers
		11	List of Tables, Figures and Listings was updated.
Addendum 5.0	30 Mar 2023	6.6	Added summary of pulmonary function at baseline
		11	List of Tables, Figures and Listings was updated.

SAP Amendments Post Final Database Lock

Version	Issue Date	Section	Revision / Addition
Post database lock	09 May 2023	6.6	Added baseline summaries by study part
		11	List of Tables, Figures and Listings was updated.

Confidentiality Statement
This document is the property of [REDACTED] and may not be duplicated, copied, altered or removed from company without prior approval from [REDACTED] or in compliance with [REDACTED].

Table of Contents

1	INTRODUCTION	7
2	STUDY OBJECTIVES	7
2.1	Primary Objective	7
2.2	Secondary Objective	7
2.3	Exploratory Objectives	7
3	ENDPOINTS	8
3.1	Primary Safety Endpoint.....	8
3.2	Secondary Pharmacokinetic Endpoints.....	8
3.3	Secondary Pharmacodynamic Endpoints.....	8
3.4	Exploratory Endpoints	8
3.4.1	Exploratory Efficacy Endpoints.....	8
3.4.2	Other Assessments or Analyses	9
4	SAMPLE SIZE	9
5	RANDOMIZATION	9
6	PLANNED ANALYSES.....	10
6.1	Analysis Populations.....	10
6.1.1	Screened Participants	10
6.1.2	Randomized Participants	10
6.1.3	Safety Population	10
6.1.4	PK Analysis Population	10
6.1.5	PD Analysis Population	11
6.1.6	Efficacy Intent-to-Treat Population	11

1 INTRODUCTION

This document details the planned statistical analyses for Pliant Therapeutics Inc., protocol number “PLN-74809-IPF-202” study titled “A randomized, double-blind, dose-ranging, placebo-controlled Phase 2a evaluation of the safety, tolerability, and pharmacokinetics of PLN-74809 in participants with idiopathic pulmonary fibrosis (IPF) (INTEGRIS-IPF)”.

The proposed analyses are based on the contents of Protocol Amendment 3, dated 19 October 2021.

This is a Phase 2a, multicenter, 4-part, randomized, double-blind, dose-ranging, placebo-controlled study to evaluate the safety, tolerability, and pharmacokinetics (PK) of once-daily (QD) treatment with PLN-74809 in participants with idiopathic pulmonary fibrosis (IPF).

Each study part consists of an up to 28-day screening period, a 4-week (Part A), 12-week (Parts B and C), or at least 24-week (Part D) treatment period, and a 2-week (±3 days) post-treatment follow-up period.

2 STUDY OBJECTIVES

2.1 Primary Objective

- Assessment of the safety and tolerability of PLN-74809.

2.2 Secondary Objective

- Assessment of PK of PLN-74809.

2.3 Exploratory Objectives

The exploratory objectives of this study are as follows:

- Assessment of change from baseline in Forced Vital Capacity (FVC)
- Assessment of change from baseline in Quantitative Lung Fibrosis (QLF) score
- Assessment of change from baseline in a visual analog scale (VAS) for cough
- Assessment of changes in selected biomarkers.

Confidentiality Statement	
This document is the property of [REDACTED] and may not be duplicated, copied, altered or removed from company without prior approval from [REDACTED] or in compliance with [REDACTED].	

[REDACTED]

Controlled Quality Management Document		
	Sponsor:	Pliant Therapeutics Inc.
	Protocol Number:	PLN-74809-IPF-202
STATISTICAL ANALYSIS PLAN. PHASE 2-3-4		

3 ENDPOINTS

3.1 Primary Safety Endpoint

The primary safety endpoint is the nature and proportion of AEs between PLN-74809 and placebo groups (descriptive).

Other safety endpoints include clinical laboratory tests (including hematology, serum chemistry, coagulation, and urinalysis), [REDACTED], vital sign measurements, changes in physical examination and concomitant medications.

3.2 Secondary Pharmacokinetic Endpoints

Plasma PLN-74809 concentrations ([REDACTED]) at each sampling timepoint will be presented in listings and descriptive summary statistics by dose and visit. The data will also be presented graphically.

3.3 Secondary Pharmacodynamic Endpoints

- Presence or actual concentration of biomarkers in urine, plasma, or serum samples.
- Levels of biomarkers markers as well as relative (and/or absolute) change in levels for each participant and the relationship between these markers.
- Relationships between PK and PD may be evaluated in an exploratory fashion and presented in graphical manner.

3.4 Exploratory Endpoints

3.4.1 Exploratory Efficacy Endpoints

- FVC including percent of predicted and absolute volume (mL).
- QLF score assessed by high-resolution computerized tomography (HRCT).
- Patient-reported outcome (PRO) measured by visual analog scale (VAS) for cough.

Confidentiality Statement	
This document is the property of [REDACTED] and may not be duplicated, copied, altered or removed from company without prior approval from [REDACTED] or in compliance with [REDACTED].	

Controlled Quality Management Document		
	Sponsor:	Pliant Therapeutics Inc.
	Protocol Number:	PLN-74809-IPF-202
STATISTICAL ANALYSIS PLAN. PHASE 2-3-4		

3.4.2 Other Assessments or Analyses

██████████ concentrations of PLN-74809 will be determined in plasma samples. Exploratory metabolite evaluation may be performed in plasma samples.

4 SAMPLE SIZE

Recruitment for Part A is complete with 1 participant enrolled.

For Parts B, C and D, the sample size of approximately 21 participants receiving PLN-74809 per treatment group is expected to provide a meaningful evaluation of PLN-74809 safety, tolerability and PK in the target population.

Approximately 112 participants may be enrolled in study Parts B (n = 28), C (n = 56), and D (n=28).

5 RANDOMIZATION

In Part A, participants were randomized 1:1:1 to receive PLN-74809 (20 mg), PLN-74809 (40 mg) or Placebo. Recruitment for Part A is complete with 1 participant enrolled.

In Part B, 28 eligible participants were randomized 3:1 on Day 1 (Visit 2) to receive PLN-74809 (40 mg) or Placebo.

In Part C, 56 eligible participants per cohort will be randomized 3:3:2 on Day 1 (Visit 2) to receive PLN-74809 (80 mg), PLN 74809 (160 mg) or Placebo.

In Part D, 28 eligible participants will be randomized 3:1 on Day 1 (Visit 2) to receive PLN-74809 (320 mg) or Placebo.

Randomization will be stratified by use of Standard of Care (SoC) IPF therapy (pirfenidone or nintedanib) (SoC use; yes or no).

Assignment will be performed in a blinded manner using interactive response technology (IRT) based on a previously generated randomization code. Randomization will occur immediately prior to dosing on the morning of the first dose (Day 1).

Confidentiality Statement	
This document is the property of ██████████, and may not be duplicated, copied, altered or removed from company without prior approval from ██████████ or in compliance with ██████████.	

██████████

Controlled Quality Management Document		
	Sponsor:	Pliant Therapeutics Inc.
	Protocol Number:	PLN-74809-IPF-202
STATISTICAL ANALYSIS PLAN. PHASE 2-3-4		

6 PLANNED ANALYSES

Any statistical analysis plan (SAP) prepared in advance of final participant data cannot be definitive, therefore the Clinical Study Report (CSR) may contain additional tables or statistical tests if warranted by the data obtained. The justification for any such additional analyses will be fully documented in the final CSR.

Please note: Since study Part A is considered complete, data from the one enrolled participant in Part A will be listed only. Analyses described herein refer to analysis of data from participants taking part in study parts B, C, and D only.

6.1 Analysis Populations

Participants excluded from the analysis populations and the reason for their exclusion will be listed in Appendix 16.2 of the CSR.

6.1.1 Screened Participants

Screened Participants are any participants who gave informed consent to participate in the study.

6.1.2 Randomized Participants

Randomized Participants are any participants who were assigned a randomization number.

6.1.3 Safety Population

The Safety Population includes all randomized participants who receive at least one dose of study drug.

6.1.4 PK Analysis Population

The PK Analysis Population includes all randomized participants who have concentration data (including below the limit of quantification (BLQ)) for PLN-74809, nintedanib or pirfenidone.

Confidentiality Statement	
This document is the property of [REDACTED] and may not be duplicated, copied, altered or removed from company without prior approval from [REDACTED] or in compliance with [REDACTED].	

[REDACTED]

Controlled Quality Management Document		
	Sponsor:	Pliant Therapeutics Inc.
	Protocol Number:	PLN-74809-IPF-202
STATISTICAL ANALYSIS PLAN. PHASE 2-3-4		

6.1.5 PD Analysis Population

The PD Analysis Population includes all randomized participants who receive any amount of study drug and who have results from baseline and from at least one post-baseline PD assessment.

6.1.6 Efficacy Intent-to-Treat Population

The Efficacy Intent-to-Treat (ITT) Population includes all randomized participants.

6.1.7 Efficacy Per Protocol Population

The Efficacy Per Protocol Population will include the subset of the ITT Population who complete the study without any protocol deviations that may significantly impact the interpretation of safety and/or efficacy analyses.

6.1.8 Efficacy Modified Intent-to-Treat Population

The Efficacy modified Intent-to-Treat (mITT) Population includes all randomized participants who do not have FVC values that meet outlier criteria. [REDACTED].

6.2 Derived Data

This section describes the derivations required for statistical analysis. Unless otherwise stated, variables derived in the source data will not be re-calculated.

6.2.1 Race

Where more than one race category has been selected for a participant, these race categories will be combined into a single category labeled “Multiple Race” in the summary tables. The listings will reflect the original selected categories.

6.2.2 Body Mass Index

Body mass index (BMI) will be calculated as follows:

$$\text{BMI (kg/m}^2\text{)} = \text{Weight at Screening (kg)} / [\text{Height at Screening (m)}^2]$$

Confidentiality Statement	
This document is the property of [REDACTED] and may not be duplicated, copied, altered or removed from company without prior approval from [REDACTED] or in compliance with [REDACTED].	

Controlled Quality Management Document		
	Sponsor:	Pliant Therapeutics Inc.
	Protocol Number:	PLN-74809-IPF-202
STATISTICAL ANALYSIS PLAN. PHASE 2-3-4		

6.2.3 Baseline

In general, baseline is defined as the last non-missing value (either scheduled, unscheduled or repeat) before the participant receives the first dose of study drug, unless otherwise specified.

6.2.4 Early Termination Assessments

Early termination assessments will not be summarized. Early termination assessments will appear in the listings as recorded.

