8.7 Clinical Laboratory Adverse Events

Abnormal laboratory findings (eg, clinical chemistry, hematology and urinalysis) or other abnormal assessments (eg, ██████, vital signs) per se are not reported as AEs. However, those abnormal findings that are deemed clinically significant or are associated with signs and/or symptoms must be recorded as AEs if they meet the definition of an AE, as described in [Section 8.2](#) (or recorded as an SAE if they meet the criteria of being serious, as described in [Section 8.8](#)). Clinically significant abnormal laboratory or other abnormal findings that are detected after consent or that are present at baseline and worsen after consent are included as AEs (and SAEs if serious).

The Investigator should exercise his/her medical and scientific judgment in deciding whether an abnormal laboratory finding or other abnormal assessment is clinically significant. Usually, the abnormality should be associated with a clinically evident sign or symptom, or be likely to result in an evident sign or symptom in the near term, to be considered clinically significant. A clinically significant laboratory abnormality in the absence of clinical symptoms may jeopardize the participant and may require intervention to prevent immediate consequences. For example, a markedly low serum glucose concentration may not be accompanied by coma or convulsions, yet be of a magnitude to require glucose administration to prevent such sequelae.

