8.8.2 Recording Adverse Events and Serious Adverse Events

All AEs and SAEs spontaneously reported by the participant and/or in response to an open question from study personnel or revealed by observation, physical examination or other diagnostic procedures will be recorded on the appropriate page of the eCRF. Any clinically relevant deterioration in laboratory assessments or other clinical finding is considered an AE and must be recorded on the appropriate pages of the eCRF. When possible, signs and symptoms indicating a common underlying pathology should be noted as one comprehensive event.

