12.5 Primary Endpoints

12.5.1 *Primary Safety Endpoint*

- Nature and proportion of AEs between PLN-74809 and placebo groups (descriptive)

Safety data from all participants who received at least one dose of study drug will be incorporated into the final safety analysis. Further details of the safety analyses will be

provided in the SAP. AEs will be collected from the time the participant signs the ICF until the last study visit. Treatment-emergent adverse events (TEAEs) are defined as AEs that emerged or worsened in severity after the first administration of study drug.

AEs will be coded using the Medical Dictionary for Regulatory Activities (MedDRA[®]). All AEs will be graded for severity per the CTCAE grading scale and listed by participant and summarized by last treatment taken at onset of AE. All AEs will be listed by participant and summarized by last treatment taken at onset of AE.

The incidence of AEs, the incidence of TEAEs, the incidence of treatment-related AEs, and the severity of AEs will be summarized by system organ class, preferred term, and maximum severity. In cases where a participant reports multiple occurrences of the same event (preferred term), the greatest severity will be included in the summary. The number and percentage of participants with SAEs and treatment-related SAEs and participants who withdraw prematurely due to an AE will be tabulated by study treatment and dose.

Clinical laboratory test parameters will be graded using the CTCAE grading scale for individual participants and values outside the reference ranges will be flagged. The incidence of treatment-emergent laboratory abnormalities will be summarized by severity and treatment group. For each parameter, summary statistics will be calculated for each measure and summarized by treatment and dose.

Individual [REDACTED] results will be listed for each participant. Summaries of [REDACTED] by treatment and dose will include changes from baseline for each parameter.

Vital sign measurements other laboratory tests, concomitant medications, medical history and changes in physical examinations at each time point will be listed by participant. The number and percentage of participants with abnormal [REDACTED] will be summarized by treatment and dose.

Concomitant medications will be coded using the most current World Health Organization drug dictionary available.

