6.2.8 Unscheduled Visits

Only scheduled post-baseline values will be tabulated. Post-baseline repeat / unscheduled assessments will not be summarized but will be listed in the relevant appendices to the CSR.

Controlled Quality Management Document		
	Sponsor:	Pliant Therapeutics Inc.
	Protocol Number:	PLN-74809-IPF-202
STATISTICAL ANALYSIS PLAN. PHASE 2-3-4		

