6.15.2 Laboratory Data

Descriptive statistics of the observed values and change from baseline will be presented by treatment group and visit for each continuous hematology, serum chemistry, coagulation, and urinalysis parameter. Shift tables for the change from baseline in categorical parameters will be presented in the natural order of the outcome where possible.

Summaries and listings will be presented using the Système International (SI) unit for each parameter as received from the analytical laboratory.

Each measurement (for continuous data and for categorical data where provided) will be classed as below, within, or above normal range, based on ranges supplied by the laboratory used. Shift tables in relation to the normal range from baseline to each follow-up visit will be presented.

In addition, any confirmed liver abnormalities, identified per Section 6.2.19, will be summarized by treatment group and listed.

All individual laboratory data (including pregnancy testing data) will be listed. Any liver abnormalities identified will be provided as a separate listing.

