9 CHANGES TO PLANNED PROTOCOL ANALYSIS

1. Adverse event summaries and efficacy assessments will be presented overall and [REDACTED]
2. Change from Baseline at Week 12 in efficacy assessments will also be presented by [REDACTED]

QMD [REDACTED]	
Confidentiality Statement	
This document is the property of [REDACTED] and may not be duplicated, copied, altered or removed from company without prior approval from [REDACTED] or in compliance with [REDACTED].	

Controlled Quality Management Document		
	Sponsor:	Pliant Therapeutics Inc.
	Protocol Number:	PLN-74809-IPF-202
STATISTICAL ANALYSIS PLAN. PHASE 2-3-4		

3. [REDACTED]
4. A mixed model for repeated measures [REDACTED].
5. Definition of Efficacy Per Protocol Population was revised from:
[REDACTED]
6. Removed CTCAE grading summaries for laboratory test parameters.
[REDACTED]
8. Added additional pooled placebo groups for comparison purposes.

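### The SAP drops the protocol's laboratory severity summary and keeps early-termination and unscheduled values out of its tables, so some marked non-liver values are counted nowhere

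*SAP*

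**What the plan says.** Protocol 12.5.1, the primary safety endpoint section, has laboratory parameters graded by CTCAE for each participant and then commits to a table: "The incidence of treatment-emergent laboratory abnormalities will be summarized by severity and treatment group".

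The SAP takes this out. The amendment table, under Addendum 1.0 (02 Dec 2022, after the Parts A/B/C Week 12 lock and before the Part D Week 12 lock), records "CTCAE grading for laboratory test parameters removed". SAP 9 declares the same change: "Removed CTCAE grading summaries for laboratory test parameters".

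What SAP 6.15.2 keeps is descriptive statistics by visit, shift tables for categorical results, classification as below, within or above the normal range ("Shift tables in relation to the normal range from baseline to each follow-up visit will be presented"), a summary of confirmed liver abnormalities, and a listing of all laboratory data.

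Two general conventions limit which values reach any table. SAP 6.2.4: "Early termination assessments will not be summarized". SAP 6.2.8, after restricting tabulation to scheduled post-baseline values: "Post-baseline repeat / unscheduled assessments will not be summarized but will be listed in the relevant appendices to the CSR".

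**The concern.** Safety and tolerability are the primary objective, and the protocol chose a summary that does not depend on anyone's opinion of a laboratory value: grade it, then count participants by grade and group. The visible SAP has no equivalent for non-liver parameters. A normal-range shift puts a slightly low value and a severely low value in the same cell.

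The scheduled-only conventions widen the gap. Protocol 11 names a clinically significant laboratory change among the reasons for stopping study drug or leaving the study, and has early-termination assessments follow. Unscheduled tests are also a natural place for marked values to appear. SAP 6.2.3 lets unscheduled and repeat values serve as baseline, so the restriction applies only after dosing, when harm would show.

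At stake is whether a reader of the report can see how many participants in each dose group had a marked laboratory abnormality.

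**Working it through.** The plan states no figure on this point, so there is none to reproduce. The check is a comparison of texts, followed by arithmetic for scale.

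**Where a marked non-liver value can appear under the visible SAP**

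| Where the value was seen | Reported as an AE | Not reported as an AE |
|---|---|---|
| Scheduled visit | AE tables by grade (SAP 6.15.1); by-visit statistics and shifts | By-visit statistics and shifts; no count by severity |
| Early-termination or unscheduled visit | AE tables by grade | Listing only |

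- By-visit minimum and maximum (SAP 6.3.4) show how extreme one scheduled value was. They do not say how many participants reached a given severity, and they give no worst value per participant.
- The right-hand column can be occupied. Protocol 8.7 says abnormal findings are not AEs in themselves and leaves the decision to the site: "The Investigator should exercise his/her medical and scientific judgment in deciding whether an abnormal laboratory finding or other abnormal assessment is clinically significant".

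**Share of a group that one participant represents**

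Inputs: part sizes 28, 56 and 28 with ratios 3:1, 3:3:2 and 3:1 (Protocol 6.4).

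- Active per dose: 28 × 3/4 = 21 (Part B); 56 × 3/8 = 21 for each dose in Part C; 28 × 3/4 = 21 (Part D). Total 4 × 21 = 84.
- Placebo: 28/4 + 56 × 2/8 + 28/4 = 7 + 14 + 7 = 28.
- These match the 21 per dose level in Protocol 12.2 and the 84 and 28 in Protocol 3.1.
- One participant: 1/21 = 4.8%; 1/28 = 3.6%; 1/84 = 1.2%.

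**Nominal intervals between scheduled draws** (Protocol Appendices 1 and 2, visit days)

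- Parts B and C: 56 − 28 = 28 days; 84 − 56 = 28 days.
- Part D: 140 − 98 = 42 days; 224 − 182 = 42 days; 280 − 224 = 56 days.

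Within these intervals the only possible laboratory results are unscheduled or early-termination ones.

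**Illustration under assumed rates (not from the documents)**

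Let p be the true incidence of a severe abnormality and s the share of cases seen only off schedule. The chance that a dose group of 21 has at least one case is 1 − (1 − p)^21. If a severity table took scheduled values only, the chance that it shows at least one case is 1 − (1 − p(1 − s))^21.

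| p | All visits | Scheduled only, s = 0.25 | Scheduled only, s = 0.5 |
|---|---|---|---|
| 5% | 65.9% | 55.2% | 41.2% |
| 10% | 89.1% | 80.5% | 65.9% |
| 15% | 96.7% | 91.8% | 80.5% |

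So if the severity table is restored, it matters which visits feed it.

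**The case against.** **The removal is disclosed, and the protocol leaves safety-analysis detail to the SAP.** True. This is a documented departure and nothing is hidden. But the severity summary was a specific commitment, and no reason for dropping it is visible.

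**The AE tables cover the important cases.** Largely true. Protocol 8.8.2 says "Any clinically relevant deterioration in laboratory assessments or other clinical finding is considered an AE and must be recorded", and SAP 6.15.1 tabulates AEs by grade and several by their effect on study drug. SAP 6.4 summarises reasons for not completing treatment and for early termination. A laboratory change serious enough to stop treatment should reach those tables. What remains is the value the investigator does not judge clinically significant. Objective grading is useful there because it does not rest on that judgement.

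**The primary endpoint is untouched.** Correct. SAP 3.1 defines it as the nature and proportion of AEs and places laboratory tests among the other safety endpoints. The loss is to the laboratory part of the safety evaluation.

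**Blacked-out text may hold the answer.** The SAP table list, part of SAP 6.2 and a block in SAP 9 directly after the item on grading are unreadable. A reason or a further table cannot be ruled out, so the conclusion covers visible text only.

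**The protocol never required unscheduled or early-termination values in the summary.** Also correct. Using them improves on the protocol text. Scheduled-only tables have a sound rationale, since testing frequency differs between participants, and by-visit tables should stay that way.

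**The off-schedule share may be small.** Haematology, chemistry and coagulation are drawn at every scheduled visit shown, and Protocol 3.1 asks participants who stop drug for safety reasons to stay for the rest of the visits. This limits the gap by an unknown amount.

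**Conclusion.** The point holds. Following the visible SAP, non-liver laboratory abnormalities that are not reported as AEs have no incidence by severity in any treatment group, although the protocol planned one. Those seen only at early-termination or unscheduled visits enter no visible laboratory table.

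The size cannot be estimated from the documents. Each such participant is worth 4.8 percentage points of a dose group, 3.6 of pooled placebo and 1.2 of all active participants, taking the planned numbers as achieved. The data are listed and the primary AE analysis is intact, so this should be corrected but does not undermine the trial.

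The conclusion assumes that the blacked-out parts contain no equivalent table. It also depends on which results after stopping drug count as scheduled, and here the protocol is not consistent. Section 3.1 keeps participants who stop for safety reasons in follow-up, with an early-termination visit only if that cannot be done. Section 11 sends anyone who stops drug to early-termination assessments.

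**What to change.** 1. In SAP 6.15.2, restore the summary of treatment-emergent laboratory abnormalities by severity and treatment group. Base it on each participant's worst post-baseline value per parameter, from all scheduled, unscheduled and early-termination results. Use the CTCAE grade where one exists and the normal-range class otherwise.
2. In SAP 6.2.4 and 6.2.8, name this table as the one exception. Leave the by-visit tables on scheduled values only.
3. If the severity summary stays out, give the reason in SAP 9. This is the weaker option, because it explains the gap without closing it.
4. Reconcile Protocol 3.1 with Protocol 11, so that it is clear which assessments apply after study drug is stopped and how their results are classified.

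The cost is SAP wording and one table programmed from data already collected and listed. SAP 6 allows additional tables in the study report if they are justified. The drawback is that participants tested more often have more chances of an abnormal result, so footnote the number of tests per participant by group.
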